10.3 Definitions

10.3.1 An **adverse event (AE)** is any untoward medical occurrence, undesirable medical condition, recurrence or deterioration of a preexisting medical condition, or disease temporally associated with or subsequent to exposure to a pharmaceutical product/treatment or protocol-imposed intervention, regardless of attribution. This includes signs (including a clinically significant abnormal laboratory finding), symptoms or condition occurring at any dose independent of perceived causal relationship to the product or treatment. AEs may or may not be formal medical diagnoses. Common examples include nausea, chest pain, tachycardia, enlarged liver, or electrocardiogram abnormalities.

10.3.2 **Inter-current illness** or injuries should be regarded as adverse events.

Abnormal results of diagnostic procedures are considered to be adverse events if the abnormality:

- Results in study withdrawal.
- Is associated with a serious adverse event.
- Is associated with clinical signs or symptoms.
- Leads to additional treatment or to further diagnostic tests.
- Is considered by the Investigator to be of clinical significance.

10.3.3 A ***serious adverse event (SAE)*** as defined by the International Conference on Harmonization (ICH) is any adverse experience that at any dose meets any of the following conditions:

- Results in death (i.e., the adverse event causes or leads to death).
- Is life-threatening.
- Requires inpatient hospitalization or prolongation of existing hospitalization.
- Results in persistent or significant disability/incapacity.
- Results in a congenital anomaly/birth defect.
- An important medical event that may not result in death, be life-threatening, or require hospitalization may be considered a serious adverse drug reaction when, based upon appropriate medical judgment, they may require medical or surgical intervention to prevent one of the outcomes listed in the definition above. Examples of such medical events includes allergic bronchospasms requiring intensive treatment in an emergency room or at home, blood dyscrasias or convulsions that do not result in inpatient hospitalization, or the development of drug dependency or drug abuse.

10.3.4 ***Life-threatening*** refers to immediate risk of death as the event occurred per the view of the investigator. A life-threatening experience does not include an experience, had it occurred in a more severe form, might have caused death, but as it actually occurred, did not create an immediate risk of death. For example, hepatitis that resolved without evidence of hepatic failure would not be considered life-threatening, even though hepatitis of a more severe nature can be fatal. Similarly, an allergic reaction resulting in angioedema of the face would not be life-threatening, even though angioedema of the larynx, allergic bronchospasm, or anaphylaxis can be fatal.

10.3.5 ***Hospitalization*** is official admission to a hospital. Hospitalization or prolongation of a hospitalization constitutes criteria for an AE to be serious; however, it is not in itself considered an SAE. In absence of an AE, a hospitalization or prolongation of a hospitalization should not be reported as an SAE by the participating investigator. This is the case in the following situations:

- The hospitalization or prolongation of hospitalization is needed for a procedure required by the protocol (drug administration, protocol-requiring testing, etc.).
- The hospitalization or prolongation of hospitalization is part of a routine procedure followed by the center (e.g., stent removal after surgery). This should be recorded in the study file.
- Social admissions (e.g., subject has no place to sleep).
- Administrative admissions (e.g., for yearly physical examinations).
- Admission for treatment of a preexisting medical condition not associated with the development of a new adverse event or with a worsening of the preexisting condition.
- Optional admission not associated with a precipitating clinical adverse event (e.g., for elective cosmetic surgery).

In addition, a hospitalization for a preexisting condition that has not worsened does not constitute an SAE. Hospitalization does not include the following: rehabilitation facilities, hospice facilities, respite care (e.g., caregiver relief), skilled nursing facilities, nursing homes, routine emergency room admissions, or same day surgeries. Diagnostic and therapeutic non-invasive procedures, such as surgery, should not be reported as adverse events. However, the medical condition for which the procedure was performed should be reported if it meets the definition of an adverse event. For example, an acute appendicitis that begins during the adverse event reporting period should be reported as the adverse event, and the resulting appendectomy should be recorded as treatment of the adverse event.

10.3.6 **Disability** is defined as a substantial disruption in a person's ability to conduct normal life functions. If there is any doubt about whether the information constitutes an SAE, the information is treated as an SAE.

10.3.7 **Congenital Anomaly/Birth Defect** in a neonate/infant born to a mother exposed to the investigational or pharmaceutical product/treatment.

10.3.8 A **protocol-related AE** is an AE occurring during a clinical study that is not related to the test article, but is considered by the investigator or the medical monitor (or designee) to be related to the research conditions, i.e., related to the fact that a subject is participating in the study. For example, a protocol-related AE may be an untoward event occurring during a washout period or an event related to a medical procedure required by the protocol.

***All adverse events should be noted on the Adverse Reaction case report form (CRF), whether or not is felt to be related to study drug.

10.3.9 **Related/Associated** (with the use of the drug): There is a reasonable

possibility (more likely than not) that the event may have been caused by the drug, device or research. Determining the possible cause of an event includes assessing temporal relationships, dechallenge/rechallenge information, association (or lack of association) with underlying diseases, and the presence (or absence) of a more likely cause.

10.3.10 An **unexpected adverse** event means any adverse event that is not identified in nature, severity, or frequency in the current Investigator Brochure.

10.3.11 **Overdose** is defined as the accidental or intentional ingestion of any dose of a product that is considered both excessive and medically important. An overdose is defined as a dose increase of Nintedanib other than one prescribed by a health care professional or recommended by this protocol, whether accidental or intentional. For reporting purposes overdose does not need to be reported to Boehringer Ingelheim unless there is an SAE associated with the overdose. An overdose itself does not meet any criteria for reporting to BI (Safety) as an AE/SAE. If an SAE occurs due to overdose, the SAE should be reported and the information should be reported and the information should be reflected in the administration section of the SAE form.

10.3.12 A **pre-existing condition** is one that is present at the start of the study, and should be recorded as an adverse event if the frequency, intensity, or the character of the condition worsens during the study period.

10.3.13 **Seriousness** is a regulatory definition and is based on patient or event outcome or action criteria usually associated with events that pose a threat to a patient's life or functioning. Seriousness (not severity) serves as the guide for defining regulatory obligations from the Sponsor to applicable regulatory authorities.

10.3.14 **Severity** (or intensity) refers to the grade of a specific AE (e.g., mild (grade 1); moderate (grade 2); or severe (grade 3) myocardial infarction); see table for further details.

***Severity and seriousness should be independently assessed when recoding AEs and SAEs on the CRF.*

10.3.15 **Non-Serious AEs** are any events that do not meet any of the criteria for Serious.

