1	Mild; asymptomatic or mild symptoms; clinical or diagnostic observations only; intervention not indicated.	Transient or mild discomfort (< 48 hours); no interference with the subject's daily activities; no medical intervention/therapy required
2	Moderate; minimal, local or noninvasive intervention indicated; limiting age-appropriate instrumental ADL*	Mild to moderate interference with the subject's daily activities; no or minimal medical intervention/therapy required
3	Severe or medically significant but not immediately life-threatening; hospitalization or prolongation of hospitalization indicated; disabling; limiting self-care ADL**	Considerable interference with the subject's daily activities; medical intervention/therapy required; hospitalization possible
4	Life-threatening consequences; urgent intervention indicated.	Extreme limitation in activity; significant medical intervention/therapy required, hospitalization probable
5	Death related to AE	Death related to AE

Causal relationship of adverse event

Medical judgment should be used to determine the relationship, considering all relevant factors, including pattern of reaction, temporal relationship, de-challenge or re-challenge, confounding factors such as concomitant medication, concomitant diseases and relevant history. Assessment of causal relationship must be recorded for each adverse event.

Causality will be reported as either “Yes” or “No”.

Yes: There is a reasonable causal relationship between the investigational product administered and the AE.

No: There is no reasonable causal relationship between the investigational product administered and the AE.

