Information for final description and evaluation of a case report may not be available with the required time frames for reporting. Nevertheless, for regulatory

purposes, initial report shall be submitted within the prescribed time as long as the following minimal requirements are met:

The ***initial*** report for each SAE should include at minimum the following information:

- Protocol # and title.
- Regulatory Seriousness criteria if applicable (i.e., death; life-threatening; hospitalization; etc.).
- Patient initials, study identification number, sex, and age.
- Date the event occurred (onset).
- Severity (intensity) - see chart.
- Description of the SAE.
- Dose level and cycle number at the time the SAE occurred.
- Description of the patient's condition.
- Indication whether the patient remains on study.
- Causality (relationship of the event to the study medication).

Follow-up information may include:

- Severity (intensity) - see chart.
- Duration of the event.
- Treatment and/or medication(s) given for the event, if any.
- Brief narrative summarizing the relevant details of the event.
- Action taken to study medication.
- Concomitant medications.
- Event outcome with dates should be communicated to the Duke as soon as possible.
- When applicable and requested, information from relevant hospital records (e.g., discharge summary, autopsy reports, etc.).

Upon receipt of the Serious Adverse Event Report Form by Duke, DCI Safety will:

- a. Notify [name] of the event via email and obtain an assessment for each event via the SAE Review Form.
- b. Fax the form to Boehringer Ingelheim Global Pharmacovigilance Center US (GPV Centre US) at [name]

All adverse events, regardless of severity, and whether or not ascribed to the study drug administration, will be recorded in the appropriate section of the Case Report Form. Patients withdrawn from the study due to AEs will be followed by the Investigator until the outcome is determined and, when appropriate, additional written reports and documentation will be provided.

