10.12 Regulatory (Expedited) Reporting

As per 21 CFR 312.2(a), this study must be conducted under an IND. [name] [name] of Duke University Medical Center will be the sponsor-investigator for this study and will hold the IND. Thus, [name] will serve as both a principal investigator and the regulatory sponsor of this multi-center study.

Per 21 CFR 312.32(c), the sponsor will notify the FDA and all participating investigators in a written IND Safety Report of:

- (A) Any adverse event associated with the use of the drug
- (B) That is both serious and unexpected (see above for definitions).

- Each notification shall be made as soon as possible and in no event later than 15 calendar days after the sponsor's initial receipt of the information. Each written notification may be submitted on FDA Form 3500A (MedWatch form) or in a narrative format. In each written IND safety report, the sponsor shall identify all safety reports previously filed with the IND concerning a similar adverse experience, and shall analyze the significance of the adverse experience in light of the previous, similar reports.
- The sponsor shall also notify the FDA by telephone or by fax of any unexpected fatal or life-threatening experience associated with the use of the drug as soon as possible but no later than 7 calendar days after the sponsor's initial receipt of the information.
- Follow-up information to a safety report shall be submitted as soon as the relevant information is available.
- Additionally, adverse events will be reported to the FDA in an annual report according to annual report requirements. Events will be reviewed and reported to the Duke IRB according to local IRB guidelines.

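### Section 10.3.9 joins two causality thresholds in wording that 10.12 shares, so an event possibly but not probably caused by the drug could miss 7- or 15-day notice

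*Combined protocol and SAP*

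**What the plan says.** Four places in section 10 of the combined protocol and SAP bear on this.

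- **10.3.9 (definition).** The Related/Associated entry runs over a line break. It opens "with the use of the drug): There is a reasonable" and continues "possibility (more likely than not) that the event may have been caused by the drug, device or research". It then lists factors to weigh: timing, dechallenge and rechallenge, underlying disease, and whether some other cause is more likely.
- **10.10 (recording).** "Assessment of causal relationship must be recorded for each adverse event". The answer is Yes or No, and Yes means: "There is a reasonable causal relationship between the investigational product administered and the AE". No probability is attached.
- **10.11 (SAE handling).** The initial SAE report must include "Causality (relationship of the event to the study medication", and the safety desk must notify the sponsor-investigator and "obtain an assessment for each event via the SAE Review Form".
- **10.12 (expedited reporting).** Citing 21 CFR 312.32(c), it says "the sponsor will notify the FDA and all participating investigators in a written IND Safety Report of" events that meet two conditions: (A) "Any adverse event associated with the use of the drug", and (B) being serious and unexpected, with a pointer back to the definitions. The limit is 15 calendar days. A separate telephone or fax notice to the FDA, within 7 calendar days, covers unexpected fatal or life-threatening experiences and carries the same association condition.

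**The concern.** A reasonable possibility can lie well below an even chance; the parenthesis in 10.3.9 cannot. One definition therefore states two thresholds, and the stricter one is absent from the assessment in 10.10. Both expedited triggers in 10.12 repeat the wording of the term that 10.3.9 defines. An assessor who looked up that term would find the parenthesis and might withhold notice of an event that an assessor using 10.10 would send.

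Uncertain attribution is foreseeable here. Section 2.4 says that class-effect events such as hypertension, proteinuria and thromboembolism, at the low frequencies seen in the phase I monotherapy trials, may not be separable from background in advanced cancer. Section 11.1 describes a single-arm trial, so no control group will settle causality later. Under 10.3.10 an event is unexpected if its severity or frequency, not only its nature, goes beyond the Investigator Brochure. Serious, unexpected events that are possibly but not probably drug-caused could therefore arise. At stake is prompt notice to the FDA and to the investigators at other sites.

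**Working it through.** The plan gives no figure to reproduce, so the check compares the texts.

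**Step 1: do the two halves of 10.3.9 agree?** Let p be the assessor's probability that the drug caused the event. On a plain reading the parenthesis requires p > 0.50. A reasonable possibility has no stated number. Take p between 0.20 and 0.50 as an illustration; this range is an assumption, not a figure from the documents. Such an event fails the parenthesis and can still be a reasonable possibility.

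**Step 2: what follows for one event?** Take a serious, unexpected event with p in that range, and suppose the assessor following 10.10 answers Yes.

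| | 10.3.9 with the parenthesis | 10.10 |
|---|---|---|
| Causality | Not related | Yes |
| Condition (A) of 10.12, if this test is used | Not met | Met |
| 15-day written report | Not triggered | Triggered |
| 7-day notice, if fatal or life-threatening | Not triggered | Triggered |

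**Step 3: does 10.3.9 reach 10.12?** Both triggers repeat the phrase that forms part of the defined term, and no other place in the documents defines it. There is no explicit cross-reference. The connection rests on matching words.

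**Step 4: does another rule settle the conflict?** The in-case-of-doubt rule in 10.3.6 concerns whether an event is an SAE, not whether the drug caused it. The uncertainty rule in 10.6 concerns disease progression. Nothing says that 10.10 overrides 10.3.9, or the reverse.

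**Step 5: what stays intact?**
- Within the reporting period, an SAE from any cause goes to the safety desk within 24 hours (10.0), and the safety desk forwards it to the supplier (10.11).
- Unexpected events on treatment or within 30 days after it go to the lead site within 24 hours, with no causality condition (10.11).
- The events of special interest in 10.4 follow the SAE timeline even when not serious.
- The sponsor-investigator tabulates adverse events continuously, and the Safety Oversight Committee reviews safety data annually (10.13).
- Adverse events also go into the annual FDA report (10.12).

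The step exposed is the next one, from sponsor to FDA and to the other sites. For those sites the documents name no other event-by-event route; 4.1 gives them the most recent Investigator Brochure.

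**Step 6: size.** The documents give neither a rate of serious unexpected events nor a distribution of p, so no count of affected events can be derived.

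**The case against.** The strongest reply is that 10.12 presents its duty as the regulation's own. Its association condition can be read as the regulation's term, with no local gloss imported, and its pointer to definitions sits on condition (B), not (A). Section 10.10 is also the assessment that must be recorded for every event, and no text tells an assessor to record the 10.3.9 category. The wording of 10.3.9 is itself hedged, since it speaks of what the drug may have caused. All of this stands. It shows that the strict reading is not compelled. It does not remove the conflict, because 10.3.9 remains the only definition of the phrase and nothing ranks the two tests.

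Three stronger readings are tempting and unsupported:

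- A reader might infer that the plan requires the stricter test for FDA notices. It does not; the link is verbal only.
- A reader might infer that the SAE forms leave the test open. The SAE Reporting Form is in the Procedure Manual and the SAE Review Form is not reproduced, so their content is unknown.
- A reader might infer a long measured delay. Assuming a 365-day annual-report interval, the most an event left to that report could lag is 365 − 15 = 350 days past the 15-day limit, or 365 − 7 = 358 days past the 7-day limit. The lag is near zero for an event just before the report. These are subtractions from an assumed interval and apply only to an event already coded as not associated because of the parenthesis. They are not evidence of impact.

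**Conclusion.** The concern holds as a conditional one. Section 10.3.9 states two thresholds, conflicts with 10.10, and shares its wording with both triggers in 10.12. If the parenthesis were applied, expedited notice of a serious, unexpected, possibly drug-caused event could be withheld from the FDA and the other sites.

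This rests on two assumptions: that the parenthesis means a probability above one half, and that whoever decides on notice takes the meaning of association from 10.3.9. Neither is certain. How many events would be affected, possibly none, is unknown. The point is a definitional inconsistency in safety reporting and touches no endpoint, analysis, dose or efficacy stopping rule. A reader should not infer that safety information would be lost: it still reaches the sponsor promptly, and only the speed of onward notice is in question. The correction is worth making because it is cheap and the exposed step concerns safety.

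**What to change.** Delete the four-word parenthesis from 10.3.9. Add one sentence, in 10.10 or 10.12, stating that 10.3.9, 10.10 and 10.12 all use a single test: whether there is a reasonable possibility of a causal relationship with the drug, recorded Yes or No.

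The cost is a short wording amendment. Design, endpoints and sample size do not change. The downside is possibly a few more expedited reports.

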10.4 Adverse Events and Laboratory Values of Special Interest

Adverse events of special interest are to be reported using the same time line as Serious Adverse Events, even if they do not meet any of the seriousness criteria:

1. **Any gastrointestinal and non-gastrointestinal perforation, leakage, fistula formation, and abscess.** In such case, the following additional information need to be collected, documented on the eCRF page and forwarded to Boehringer Ingelheim:
 - Location/extent of abdominal tumor magnifications.
 - Imaging and reports (CT, ultrasound, endoscopy, pathology, etc.).
 - Prior surgery (location, wound healing complications).
 - Concomitant diseases with GI involvement (e. g. Crohn's, vasculitis, tuberculosis, diverticulitis).
2. **Elevated transaminases:** based on laboratory values.
 - (i) ALT and/or AST $> 5x$ ULN without bilirubin elevation.
 - (ii) ALT and/or AST $> 3x$ ULN with bilirubin $> 1.5x$ ULN.
 - (iii) Occurrence of at least two (2) elevated results no more than 2 weeks apart that is not considered to be an adverse event.

In such case, the following additional information needs to be collected, documented as an adverse event or medical history if applicable, and included on the Boehringer Ingelheim SAE reporting form:

- Hepatic tumor involvement.
- Gilbert syndrome.
- Viral hepatitis (e.g., Hepatitis A; B; C; EBV; CMV).
- Alcohol and/or autoimmune hepatitis.
- Hepatobiliary disorders (e.g., gallstones).
- Vascular hepatitis conditions (e.g., portal vein thrombosis, right heart failure).
- Recent alcohol consumption.
- Recent intake of hepatotoxic compounds (including steroids).
- Other etiology.

Medical evaluation of these results and clinical documentation should be provided.

10.5 Medication Errors

Generally, medication errors are the result of administration or consumption of the wrong product, by the wrong subject, per the wrong route, at the wrong time or at the wrong dosage strength, due to human error. FDA and EMEA have adopted risk management guidance documents suggesting collection and review of medication errors in pre-approval clinical trials. The purpose of collecting and reviewing medication errors occurring in pre-approval is mainly to determine whether medication errors can be prevented prior to or after market approval. That is, the reported medication errors should be analyzed to determine whether clearer labeling, dosing instructions or packaging might have prevented the medication error. Consequently, the intention is to ensure that the improvements in labeling, dosing and/or packing clarity are implemented in the marketed

version of the product. Medication errors are reportable only as defined in the protocol. Follow the guidance below.

- a. For studies with two or more treatment arms (e.g., double blind studies), the administration or consumption of the unassigned treatment is always a reportable medication error.
- b. Administration of an expired product should be considered as a reportable medication error when associated with an AE, or if otherwise appropriate, please define for your study.
- c. For parenteral products, define reportable errors involving rate of administration and reconstitution and dilution, including use of appropriate diluent and the time frame in which test article should be used after reconstitution and/or dilution.
- d. For vaccines and biologics, define in detail reportable errors related to storage or refrigeration requirements.

All AEs and SAEs must be handled as specified in this protocol whether or not they are associated with a medication error. A medication error associated with an SAE (including overdose, inadvertent exposure, and/or accidental exposure) will be reported with the SAE on the SAE form. All other medication errors will be reported by faxing the Clinical Study Medication Error Incident Report form to the fax number indicated in the [Emergency Contacts](#) section under separate cover.

